## 6.2 IMPORTANT PROTOCOL DEVIATIONS

The documentation of the iPD categories and how to handle iPDs in the analysis are done in the DV domain specifications, which is stored within the TMF in EDMS.

#### **6.3 INTERCURRENT EVENTS**

Date: 8 Apr 2024, Version 1.0

The expected intercurrent events of interest in this trial are:

- Treatment discontinuation during the MTD evaluation period due to DLT
- Treatment discontinuation during the MTD evaluation period due to other reason than DLT
- Dose reduction during the MTD evaluation period due to a DLT
- Dose reduction during the MTD evaluation period due to other reason than DLT
- Progressive disease during the MTD evaluation period
- Death during the MTD evaluation period where the death event is not a DLT
- Any events other than DLT that cause missed visits during the MTD evaluation period

The strategy for handling intercurrent events in this trial is as follows:

Modified principal stratum: This is the effect of the treatment in the principal stratum of patients who do not discontinue treatment, miss visits, progress, or die during the MTD evaluation period for any reason other than DLT. That means patients experiencing one of the

Date: 8 Apr 2024, Version 1.0

c44138015-01

Proprietary confidential information © 2024 Boehringer Ingelheim International GmbH or one or more of its affiliated companies.

following intercurrent events are excluded from the analysis: "Treatment discontinuation during the MTD evaluation period due to other reason than DLT", "Dose reduction during the MTD evaluation period due to other reason than DLT", "Progressive disease during the MTD evaluation period", "Death during the MTD evaluation period where the death event is not a DLT", "Any events other than DLT that cause missed visits during the MTD evaluation period". The intercurrent events "Treatment discontinuation due to DLT" and "Dose reduction due to DLT" will be handled using a composite strategy, that is, patients experiencing the intercurrent events "Treatment discontinuation due to DLT" and "Dose reduction due to DLT" are included in the analysis.

Refer to ICH E9 R1 (9.2) for definitions of the principal stratum strategy and the composite strategy. Table 6.3: 1 provides an overview of the intercurrent events and the respective handling strategies. The modified principal stratum strategy is applied to the primary analysis of this trial.

Table 6.3: 1 Overview of intercurrent event handling strategies for the primary analysis of the MTD

Intercurrent event	Modified principal stratum strategy	
Treatment discontinuation during the MTD evaluation period due to DLT	Composite	
Treatment discontinuation during the MTD evaluation period due to other reason than DLT	Principal stratum	
Progressive disease during the MTD evaluation period	Principal stratum	
Death during the MTD evaluation period where the death event is not a DLT	Principal stratum	
Dose reduction during the MTD evaluation period due to a DLT	Composite	
Dose reduction during the MTD evaluation period due to other reason than DLT	Principal stratum	
Any events other than DLT that cause missed visits during the MTD evaluation period	Principal stratum	

Proprietary confidential information © 2024 Boehringer Ingelheim International GmbH or one or more of its affiliated companies.

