3.3.4.4 Replacement of patients

In Arms A and B, patients withdrawn during the MTD evaluation period for a reason other than having a DLT, or who miss any dose of study medication during the MTD evaluation period, or who miss the echocardiography/MUGA scan measurements acquired on Day 1 of Cycle 2), are not evaluable for the MTD determination. These patients will be replaced if not decided otherwise by the SMC (e.g. because the number of evaluable patients for the current dose cohort is considered high enough for a dose escalation decision). Patients who experience a DLT will not be replaced.

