#### • MTD set:

The MTD set includes all treated patients who are considered evaluable as per CTP, that is, all patients who have completed the required number of administrations of BI 1387446 (and ezabenlimab in arm B) in cycle 1 and who underwent the Echo/MUGA scan in cycle 2 visit 1. In case a patient has not completed the required number of study drug administrations due to DLT(s), he/she will be considered evaluable and included in the MTD set. Patients who cross over from Arm A to Arm B will only be included in the MTD set if they are evaluable in Arm A. The MTD set will be used for the main analysis of the MTD.

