#### 7.4 PRIMARY OBJECTIVE ANALYSIS

#### 7.4.1 Main analysis

Date: 8 Apr 2024, Version 1.0

The primary endpoints of the trial are the MTD of BI 1387446 as single agent and the MTD of BI 1387446 in combination with ezabenlimab, and the respective number of patients with DLTs in the MTD evaluation period.

The number of patients with DLTs during the MTD evaluation period at each dose level will be presented. Patients who were replaced during the MTD evaluation period will be excluded from the evaluation of the MTD.

The analysis of the MTD in each treatment arm is based on a joint BLRM for both arms guided by the escalation with overdose control principle.

The MTD in each arm is defined as the highest dose that is expected to cause less than 25% risk of the true DLT rate being above or equal to 33% during the MTD evaluation period. Estimation of the MTD will be based upon the estimation of the posterior probability of the incidence of DLT in toxicity categories during the MTD evaluation period for all evaluable patients, i.e. patients in the MTD set as defined in Section 6.4.

Using the joint BLRM model specified in CTP Section 7, tables and bar charts displaying for each dose the posterior probabilities of the true DLT rates being in either the under-toxicity interval, the targeted toxicity interval or the over-toxicity interval will be produced.

The modified principal stratum strategy as defined in Section 6.3 will be applied for handling intercurrent events in the primary objective analysis. The MTD set will be used for the analysis of the primary endpoint.

Proprietary confidential information © 2024 Boehringer Ingelheim International GmbH or one or more of its affiliated companies.

The primary analysis is aligned with the estimands described in the Table 7.4.1: 1 below.

Table 7.4.1: 1 Estimands table for primary objective analysis

Estimand attribute				
Population	Patients with different types of advanced or metastatic cancer (solid tumours)			
Treatment condition(s)	BI 1387446 monotherapy or			
	BI 1387446 in combination with ezabenlimab			
Variable (outcome)	Occurrence of DLTs in the MTD evaluation period			
Handling of intercurrent events	Treatment discontinuation or dose reduction during the MTD evaluation period due to DLT: Composite – patients will be included in the analysis contributing to the analysis with their DLT			

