	Treatment discontinuation or dose reduction during the MTD evaluation period due to other reason than DLT: Principal stratum – patients will be excluded from the analysis and replaced			
	
 
Progressive disease during the MTD evaluation period:
 
Principal stratum – patients will be excluded from the analysis and replaced
 
			
	Death during the MTD evaluation period where the death event is not a DLT: Principal stratum – patients will be excluded from the analysis and replaced			
	Any events other than DLT that cause missed visits during the MTD evaluation period: Principal stratum – patients will be excluded from the analysis and replaced			
Summary measure	Posterior probability of the incidence of DLT in toxicity categories during the MTD evaluation period per dose level for all evaluable patients			

Proprietary confidential information © 2024 Boehringer Ingelheim International GmbH or one or more of its affiliated companies.

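### SAP 6.3 drops patients who progress in the MTD evaluation period from the primary analysis, while protocol 3.3.4.4 and the SAP 6.4 MTD set keep those who complete cycle 1

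*SAP*

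**What the plan says.** SAP section 6.3 names "Progressive disease during the MTD evaluation period" as an intercurrent event, separate from discontinuation and from missed visits. The population for the primary analysis is a "principal stratum of patients who do not discontinue treatment, miss visits, progress, or die during the MTD evaluation period for any reason other than DLT". Table 6.3:1 assigns the progression row to the principal stratum strategy. Table 7.4.1:1 spells out the consequence: "patients will be excluded from the analysis and replaced". Neither table exempts a patient who has completed cycle 1.

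Protocol section 3.3.4.4 gives the grounds on which a patient is not evaluable. They are "patients withdrawn during the MTD evaluation period for a reason other than having a DLT, or who miss any dose of study medication" in that period, and those without the Cycle 2 Day 1 echocardiography/MUGA. It adds: "Patients who experience a DLT will not be replaced". Progression is not a ground.

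SAP section 6.4 follows the protocol: "The MTD set includes all treated patients who are considered evaluable as per CTP". It asks for complete cycle 1 administrations and the cardiac scan, with an exception when dosing is incomplete because of a DLT. There is no progression condition. SAP section 5.1 words the same set differently, as the patients who were not replaced.

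SAP section 7.4.1 then applies both rules to one analysis: "The modified principal stratum strategy as defined in Section 6.3 will be applied for handling intercurrent events in the primary objective analysis", and "The MTD set will be used for the analysis of the primary endpoint".

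**The concern.** The rule that decides who enters the primary analysis should give one answer for each patient. Here it gives two for a patient who progresses in the period, receives every cycle 1 dose, has the Cycle 2 Day 1 cardiac scan and is not withdrawn. Section 6.4 includes that patient and section 6.3 excludes the patient. Section 5.1, read with the replacement wording in Table 7.4.1:1, sides with 6.3, so the SAP in effect carries two MTD sets.

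Such a patient has complete DLT observation. Removing the patient conditions a safety endpoint on an efficacy outcome and discards usable data from small cohorts. As the text stands, the choice would be made at programming rather than in the plan.

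**Working it through.** **1. Where the rules agree and where they differ**

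| Patient with progression in the period | Protocol 3.3.4.4 | SAP 6.4 | SAP 6.3 |
|---|---|---|---|
| Misses a cycle 1 dose or the cardiac scan, no DLT | out | out | out |
| Withdrawn in the protocol period, no DLT | out | not addressed (refers to the protocol) | out |
| Completes cycle 1 and the scan, not withdrawn | in | in | out |

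Only the last row is in conflict.

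**2. Can that row be populated?** Yes.
- Flow Chart footnote 24 places the first on-treatment tumour assessment before cycle 2 dosing, with a window of 5 days before. Progression can therefore be documented inside the period, after cycle 1 dosing.
- Protocol section 4.1.2.3 lets patients stay on treatment after initial radiological progression, under conditions.
- Protocol section 3.1.1 lets Arm A patients with progression cross over once cycle 1 is complete. Sections 3.1.1 and 7.2.2 keep their monotherapy data in the main MTD analysis, and SAP 6.4 does so if they are evaluable in Arm A.

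**3. What counts as progression?** SAP 6.3 does not say whether first or confirmed progression is meant. SAP section 7.5.2 uses confirmed progression for patients under protocol version 3 and later. After the scan at the start of cycle 2, the next scheduled one is at cycle 4. If confirmed progression is meant, fewer patients are affected within cycle 1.

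**4. When does the period end?** The protocol period is cycle 1 (3 weeks) plus the Cycle 2 Day 1 cardiac scan and related findings. SAP sections 5.1 and 6.1 end it at the first cycle 2 administration or, if none is given, 90 days after the last administration. The exact dosing days are redacted. Protocol section 5.3.1 refers to weekly administration, and SAP 5.1 implies three cycle 1 doses because the fourth opens cycle 2. If those fall on days 1, 8 and 15, the SAP period ends at 15 + 90 = day 105, against day 21. Stopping for progression after a complete cycle 1, or progression found weeks later, could then count as an excluding event.

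**5. Size for one dose level.** The plan gives no figure to reproduce. The inputs are:
- protocol Table 7:1: mean of log(alpha) ~ N(log 0.5, 2), mean of log(beta) ~ N(0, 1);
- between-trial standard deviations fixed at their prior medians, 0.25 and 0.125;
- protocol section 7: limit of 25% on the posterior probability of a DLT rate beyond 0.33.

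The table does not say whether 2 is a standard deviation (SD) or a variance, so both are shown. The reference dose is redacted, so dose-to-reference ratios of 1, 0.5 and 0.25 are assumed. There is one arm and one dose, no borrowing, and no correlation between the parameters.

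Model: logit(p) = log(alpha) + beta × log(d/d*), with posterior proportional to prior × p^x × (1 − p)^(n − x).

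Dropping one, then two, DLT-free patients from 1 DLT in 6 gives observed rates of 1/6 = 16.7%, 1/5 = 20.0% and 1/4 = 25.0%. The posterior probability of a rate of 0.33 or more is:

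| d/d* | 2 read as | 1/6 | 1/5 | 1/4 |
|---|---|---|---|---|
| 1 | SD | 0.177 | 0.248 | 0.345 |
| 1 | variance | 0.202 | 0.273 | 0.366 |
| 0.5 | SD | 0.130 | 0.188 | 0.270 |
| 0.5 | variance | 0.126 | 0.179 | 0.251 |
| 0.25 | SD | 0.110 | 0.161 | 0.235 |
| 0.25 | variance | 0.098 | 0.142 | 0.204 |

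At the reference dose, one exclusion brings the probability to the limit (0.248, just under) or over it (0.273). At the lower ratios one exclusion does not cross it. With no DLTs, going from 0/6 to 0/5 at the reference dose stays below 0.07 under either reading.

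**The case against.** Several points narrow this.

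- **Section 6.4 governs in practice.** It may, since it defines the analysis set. The progression rows in 6.3 and both tables are then wrong as written. The readable text of SAP section 4 concerns further endpoints that will not be analysed and records no deliberate change to evaluability.
- **Escalation is not affected.** This stands. A reader might infer from the word replaced in Table 7.4.1:1 that these exclusions consume recruitment places, press on the intended maximum of 8 per dose level, or alter escalation. The documents do not support that. The SAP is dated 8 April 2024 and states that development has been terminated. On-trial evaluability and replacement follow the protocol and the safety monitoring committee, and protocol section 3.1.2 lets that committee exceed the 8. The effect lies in the final analysis only.
- **Patients with both a DLT and progression.** A reader might infer that 6.3 drops them, because the progression row lacks the DLT wording of the other excluding rows. The 6.3 definition ends with an exception for DLT, and both protocol 3.3.4.4 and SAP 5.1 say DLT patients are not replaced. The point is largely covered and needs only a clarifying phrase.
- **The supplementary analysis includes everyone.** SAP 7.4.4 does take all treated patients, but it is optional and uses DLTs from the whole on-treatment period. It does not isolate this exclusion.
- **The protocol keeps these patients only by silence.** It has no sentence saying that progressors remain evaluable. Its list of grounds and its explicit retention of cross-over patients' Arm A data still point that way.
- **The 90-day rule is a different matter.** It affects all DLT counting, and how the period ends for cross-over patients is drawn in Figure 6.1:1, which is not available here. It belongs in a separate item.

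**Conclusion.** The contradiction holds, for a limited group: patients with progression in the period who complete cycle 1 dosing and the Cycle 2 Day 1 cardiac scan and are not withdrawn in the protocol period. The group is smaller if confirmed progression is meant, and larger where no cycle 2 dose is given and the 90-day end applies.

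The consequence is a smaller n in the final primary analysis and, for DLT-free patients, a higher apparent DLT rate. That is the conservative direction. One exclusion can matter at a dose with a DLT near the overdose limit, and is negligible at a dose without one. The figures rest on a single-dose simplification with assumed dose ratios. The actual model borrows across doses and arms, and the number of affected patients is not in the documents. A shift in the declared MTD might be inferred, but nothing here shows one. Severity is minor to should-fix.

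**What to change.** 1. Remove progression as a stand-alone excluding event in SAP 6.3, Table 6.3:1 and Table 7.4.1:1, so that it excludes a patient only through a protocol 3.3.4.4 criterion. If the sponsor wants to keep it, define it (first or confirmed), record it in SAP section 4 as a change from the protocol, and show the main analysis with these patients included.
2. Use one MTD set definition in SAP 5.1 and 6.4, with all three protocol criteria including withdrawal. State that patients with a DLT in the period are kept, whether or not they progress.
3. As a separate item, reconcile the 90-day end of the MTD evaluation period with the protocol period, for evaluability and for DLT counting. State how the end is derived when cycle 2 is delayed or not given.

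Items 1 and 2 cost SAP wording, plus one extra model run if the exclusion is kept. Item 3 needs a revised derivation. None needs new data or procedures.

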21. Baseline tumour-biopsy sample to be taken from the projected injected and one distinct non-injected lesion between screening and first administration of BI 1387446. Only patients considered eligible after assessment of inclusion/exclusion criteria will be subjected to the procedure. Refer to [Section 4.1.4.1](#), [4.1.4.2](#) and [5.4.2.3](#) for lesion selection. In patients crossing over from Arm A to Arm B after completion of Cycle 1, new baseline biopsies from the injected and non-injected lesion should be taken. If biopsy at C2D1 was obtained without further treatment following the biopsy in Arm A, this new baseline biopsy is not needed.
22. Biopsy at Cycle1/Day 1 to be optionally taken 5-24h post BI 1387446 administration from the injected lesion only from patients enrolled into Arm A.
23. Optional biopsy.
24. Tumour assessments should be done according to itRECIST, and should include computed tomography (CT) scans of the chest and abdomen and, if clinically indicated, imaging of any other known or suspected sites of disease (e.g. pelvis, brain) using an appropriate method (CT or magnetic resonance imaging [MRI]). The same radiographic procedure must be used throughout the trial. The baseline tumour assessments (CT/MRI) and should be performed ≤ 28 days prior to initiation of treatment. The first on-treatment tumour assessment will be done before treatment administration at Cycle 2 (a time window of -5 days is acceptable). Positron emission tomography (PET-CT) may be performed if clinically indicated based on tumour type, however, in this case a diagnostic-quality CT scan needs to be acquired as part of the PET-CT for RECIST measurements. The CT portion of a PET-CT can be used as the basis for RECIST measurements if the site has documented that a CT with appropriate radiation dose for diagnostic quality and IV/oral contrast was used (if not medically contraindicated). Subsequent on-treatment tumour assessments will be performed before treatment administration (a time window of -7 days is acceptable) in C4, C6, C8, C10, C13, C16, C19, C23, C27, C31 and at EOT.
25. After the individual patient's end of the trial the Investigator should report only any cancers of new histology and exacerbations of existing cancer, study treatment related SAEs and study treatment related AESIs of which the Investigator may become aware of and only via the BI SAE form, refer to [Section 5.2.7.2.1](#).

Clinical Trial Protocol

[figure not shown]

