Similarly, Scenarios 4 and 7 represent cases where no patient in either arm has a DLT. In these cases, the model recommends escalating to higher doses. In some cases the recommended doses exceed the protocol specified margin given by the 100% escalation rule. The next tested dose in these scenarios will always be the dose given by the 100% rule.

Scenario 2 shows that if one of 2 patients treated with the starting dose level in Arm A has a DLT, the EWOC criterion does not allow any of the pre-specified dose levels. Doses lower than [REDACTED] could be chosen in practice if agreed between sponsor and SMC. In particular, starting Arm B at the intended dose level of [REDACTED] would not be allowed based on the overdose control of the BLRM.

Scenario 3 shows the case that already the starting dose level is very toxic, with 2 out of 2 treated patients experiencing a DLT. The overdose control implemented in the model then does not allow going to any of the pre-specified doses.

Scenario 02 represents the case where one patient has been treated at the starting dose of [REDACTED] in Arm A and has experienced a DLT. Based on the BLRM the probability for overdosing at the current dose is 0.656 and the model does not allow treating further patients on 50 µg in Arm A.

In scenario 03, three patients were treated at [REDACTED] in Arm A of which only the first one experienced a DLT, i.e. no DLTs were observed in the additional two patients. In this scenario the model again does not allow any of the pre-specified dose levels, indicating that any DLT in the first cohort leads to recommended doses [REDACTED]

Only if none of the patients in the first cohort [REDACTED] experience DLT (Scenarios 04 and 4), the model allows escalation [REDACTED]. While doses up [REDACTED] Arm A and [REDACTED] in Arm B would be allowed by the EWOC principle in Scenario 4, the recommended next dose in Arm A would be [REDACTED] (due to the maximum increment of 100%) and the starting dose in Arm B would be [REDACTED]

Scenario 05 follows scenario 04 and represents the case in which three patients were treated at the second dose level [REDACTED] in Arm A. One patient experienced a DLT. In this scenario, no escalation [REDACTED] is allowed, but further patients can be treated [REDACTED]

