# 5. ENDPOINTS(S)

## **5.1 PRIMARY ENDPOINT(S)**

The main objective of this trial is to determine the maximum tolerated dose (MTD) for BI 1387446 as single agent (Arm A) and for BI 1387446 in combination with ezabenlimab (Arm B). The number of patients with Dose Limiting Toxicities (DLTs) during the MTD evaluation period will be used to determine the MTD in each arm.

The primary endpoints are:

- MTD based on number of Dose-limiting toxicities (DLTs)
- Number of patients with DLT in the MTD evaluation period

The MTD is defined as the highest dose with less than 25% risk of the true DLT rate being above 33% during MTD evaluation period. For definition of DLTs, see CTP Section 4.1.4.4.

The MTD evaluation period is defined as the first treatment cycle including echocardiographic/MUGA scan measurements acquired on Day 1 of Cycle 2.

For analyses, the MTD evaluation period will be derived as the time from the first administration of study drug to the start of the second treatment cycle, i.e. in more detail as the time from the first administration of (any) trial medication to the start of the 2nd administration of ezabenlimab or 4th administration of BI 1387446 (whatever from the latter two comes first). In the case that the 2nd administration of ezabenlimab and/or the 4th administration of BI 1387446 are not given, the MTD evaluation period ends 90 days after the last administration.

Patients who were replaced during the MTD evaluation period will not be considered for MTD determination. Patients who experience a DLT will not be replaced. The decision on replaced patients will be collected in a separate file and stored in the TMF. Patients that have not been replaced will be referred to as patients evaluable for MTD determination (MTD set).

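### SAP 6.3 excludes patients with non-DLT intercurrent events from the primary MTD analysis with no exception for those who also had a DLT, contradicting SAP 5.1 and protocol 3.3.4.4, and no rule says which prevails

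*SAP*

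**What the plan says.** SAP 6.3 defines a modified principal stratum of "patients who do not discontinue treatment, miss visits, progress, or die during the MTD evaluation period for any reason other than DLT". Patients with progression, non-DLT death, non-DLT discontinuation, non-DLT dose reduction or visits missed for a non-DLT reason are left out. Table 6.3:1 repeats the list, and Table 7.4.1:1 adds of each such group that "patients will be excluded from the analysis and replaced". Only discontinuation or dose reduction due to a DLT "will be handled using a composite strategy", for which the estimand table says that "patients will be included in the analysis contributing to the analysis with their DLT".

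Other rules retain DLT patients. SAP 5.1 states "Patients who experience a DLT will not be replaced", as does protocol 3.3.4.4, and SAP 5.1 calls the patients who were not replaced the MTD set. Protocol 3.1 updates the BLRM once patients have either had a DLT or been observed through the period without one. SAP 6.4 does not list progression as a ground for exclusion. It keeps a patient whose cycle 1 dosing was incomplete because of a DLT.

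SAP 7.4.1 names the MTD set as the analysis set and also says: "The modified principal stratum strategy as defined in Section 6.3 will be applied for handling intercurrent events in the primary objective analysis". It gives no order of precedence.

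**The concern.** Once a patient has had a DLT in the MTD evaluation period, the binary outcome is fully observed. A later progression, withdrawal or unrelated death does not make it missing. Excluding the patient discards a known event, lowers the estimated DLT rate and biases the reported MTD upward.

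The overlap can plausibly occur. Flow Chart footnote 24 says "The first on-treatment tumour assessment will be done before treatment administration at Cycle 2", so progression on that scan falls inside the MTD evaluation period. If cycle 2 is not given, SAP 5.1 extends the period to 90 days after the last administration. A patient who stops because of a DLT can then progress or die of disease while still in the period, and so meets the composite rule and the exclusion rule at once. Two programmers could follow different sections of the same SAP and report different primary results.

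**Working it through.** **Step 1: the rules side by side, for a patient with a DLT in the MTD evaluation period.**

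| Course after the DLT | SAP 6.3 and its tables | SAP 5.1 / protocol 3.3.4.4 | SAP 6.4 |
|---|---|---|---|
| Completes cycle 1 and the echo, then progression on the cycle 2 scan | Exclude and replace | Not replaced, so in MTD set | Include |
| Misses a dose or the cycle 2 echo for a non-DLT reason | Exclude and replace | Not replaced, so in MTD set | Fails: the exception covers only dosing incomplete due to a DLT |
| Stops because of the DLT, then progression or non-DLT death before the period ends | Composite and principal stratum both apply | Not replaced, so in MTD set | Include |

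In the second row, protocol 3.3.4.4 is itself not fully explicit. It calls a patient who misses a dose or the scan non-evaluable, then bars replacement of any patient with a DLT. SAP 5.1 supplies the link from not replaced to evaluable.

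**Step 2: reproduce the plan's own model figure.** Inputs are the Arm A model and Table 7:1 priors in protocol Section 7:

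- logit π(d) = log α + β·log(d/d*).
- (log α, log β) is bivariate normal with means μα and μβ, SDs τα and τβ, and correlation ρ.
- μα ~ N(log 0.5, 2), μβ ~ N(0, 1), with log-normal τ priors and ρ ~ U(−1, 1) as printed.
- P(overdose at d | data) = Σ w·1[π(d) ≥ 0.33] / Σ w over prior draws, where w = Π π(d_k)^r_k · (1 − π(d_k))^(n_k − r_k).

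The reference dose d* is redacted and so has to be assumed. The data from trial 1381-0001 and Arm B are left out. Protocol 10.5, scenario 02 (1 DLT in 1 patient at 50 µg) gives 0.656. With d* = 800 µg the calculation gives 0.656, and with d* from 500 to 1600 µg it gives 0.672 to 0.636. The figure therefore supports the model but does not pin down d*. Reading the prior's 2 as a variance gives 0.534 to 0.487 over the same range and does not reproduce it, so it is taken as an SD.

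**Step 3: direction and sensitivity, from the protocol's own scenarios.** For 1 DLT in 3 at the starting dose (scenario 03), protocol 10.5 says: "In this scenario the model again does not allow any of the pre-specified dose levels". For 0 in 2 (scenario 1) it allows escalation. The model agrees: P(overdose at 50 µg) is 0.295 for 1/3 (0.307 to 0.280 for d* of 500 to 1600 µg), above 0.25. For 0/2 it is 0.032. This shows how much one DLT weighs in a small cohort. It does not describe the final analysis.

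**Step 4: effect on the final MTD.** SAP 5.1 and 7.4.1 take the highest dose with less than 25% overdose risk. Doses of 50, 100, 200 and 400 µg are assumed where the table is redacted. The DLT patient is dropped without a substitute.

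| Data at 50, 100, 200 µg | d* | P(overdose at 400 µg), DLT kept | DLT patient dropped | Crosses 0.25? |
|---|---|---|---|---|
| 0/3, 0/3, 1/3 | 800 | 0.345 | 0.076 (0/2) | Yes |
| same | 500 | 0.451 | 0.156 | Yes |
| same | 1000 | 0.304 | 0.057 | Yes |
| same | 1600 | 0.240 | 0.033 | No |
| 0/3, 0/3, 1/6 | 800 | 0.221 | 0.044 (0/5) | No |
| same | 600 | 0.276 | 0.076 | Yes |

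The first data set has 3 + 3 + 3 = 9 patients, below the 12 per arm that protocol Section 7 requires before the MTD may be considered reached. The second has 3 + 3 + 6 = 12 and meets that minimum. For it, at d* = 800 µg, 800 µg stays blocked either way (0.481 and 0.269).

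**The case against.** The strongest reply is that 6.3 is not the only rule. DLT patients are not replaced, patients not replaced form the MTD set, and SAP 7.4.1 estimates the MTD from that set as defined in 6.4, which does not exclude for progression. A careful analyst could conclude that DLT patients stay in. A reader might infer from 6.3 alone that the plan orders DLTs to be deleted. The documents do not support that, because other sections oppose it. What stands is that nothing resolves the conflict, and that 6.4 does not rescue a DLT patient who misses a dose or the echo for another reason.

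The overlap is also narrower than the list of events suggests. Protocol 4.1.4.3 pauses treatment for events of Grade 3 or higher, so many DLT patients who stop or reduce will do so because of the DLT and are kept. That is fair, but the 90-day extension leaves those who stop exposed to a second, excluding event.

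A reader might further infer that patients were escalated on incomplete DLT data. They were not on account of this text: escalation decisions follow the protocol and the SMC, and the SAP is dated 8 April 2024, after development had been terminated. Nor can one infer how many DLTs would be lost, or that progression and DLTs go together. The documents give no progression rate at the first scan and no such association.

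Finally, DLTs remain visible in the treated-set tables and listings of SAP 7.8.1. An all-treated BLRM exists as well, but SAP 7.4.4 makes it optional, whereas protocol 7.2.2 commits to it. Neither changes the primary result.

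**Conclusion.** The point holds as an unresolved contradiction in the primary analysis. Taken literally, SAP 6.3 and its two tables remove an observed DLT from the final MTD determination, while SAP 5.1, protocol 3.3.4.4 and protocol 3.1 keep it. That conclusion rests on the text alone.

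The direction of the bias is upward; its size depends on the case. A reader might take the nine-patient example to mean that one lost DLT always changes the MTD. It does not: the twelve-patient example at the same assumed reference dose stays below 25% either way, although it crosses the limit at 600 µg. All these figures are illustrative, because the reference dose, most dose levels and the external data are redacted and Arm B is left out.

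**What to change.** State once in SAP 6.3, and mirror in 6.4, Table 6.3:1 and Table 7.4.1:1, that any patient with a DLT in the MTD evaluation period belongs to the MTD set and is counted as a DLT, whatever other intercurrent event occurs. Principal stratum exclusion and replacement then apply only to patients without a DLT. Before the final analysis, check the replacement file named in SAP 5.1 to confirm that no DLT patient is listed as replaced.

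The cost is SAP wording and one check of existing records, with no new data or patients. The MTD estimate may be more conservative than under a literal reading of 6.3.
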